SPARSE is a single-center observational study aiming to investigate if suPAR measured preoperatively and immediately after surgery can predict the risk of future complications and post-operative mortality in adults following major non-cardiac surgery.

METHODS

Design

This is a prospective observational study designed in accordance with the declaration of Helsinki. The study will be register at Clinical Trials.gov and has been approved by the Institutional Review Board of the University Hospital of Larisa, under the reference number 60580/11-12-2018.

Patient eligibility

Consecutive patients who are scheduled to undergo elective major non-cardiac surgery with expected duration ≥ 2 hours under general anesthesia will be screened for

inclusion. All operative approaches will be eligible for inclusion, including open, laparoscopic and robotic procedures. Patients fulfilling the following inclusion criteria will be included: age \geq 18 years, and American Society of Anesthesiologists' (ASA) physical status I to IV.

Exclusion criteria will be age <18 years, any infection within the previous 4 weeks, severe liver disease, patients on renal replacement therapy pre-operatively, patients who had previously received a transplant, patients with allergies, inflammatory or immune system disorders, and/or connective tissue disease including rheumatoid arthritis, ankylosing spondylitis, and systemic lupus erythematosus, administration of steroid, antipsychotic, or anti-inflammatory/immunomodulatory medication during the 3 months prior to surgery, administration of opioids during the past week, asthma, obesity ($BMI \geq 30 \text{ kg m}^{-2}$), mental disability or severe psychiatric disease, alcohol or other abuse, legal incapacity or limited legal capacity, and subjects within the exclusion period of another study.

Management of Anesthesia and Surgical Procedures

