Endotracheal intubation and anesthetic care will be performed according to our institutional routine. Intravenous induction of general anaesthesia will include midazolam 0.15-0.35 mg/kg iv over 20-30 seconds, fentanyl 1 μ g/kg, propofol 1.5-2 mg/kg, ketamine 0.2 mg/kg (intravenous bolus), and rocuronium 0.6 mg/kg. All drugs will be prepared in labelled syringes and induction will be achieved by administration of a predetermined iv bolus dose on the basis of the patient's weight and/or age. Laryngoscopy and intubation will proceed in a standard fashion, while the position of the endotracheal tube will be confirmed by auscultation and

capnography/capnometry. The patients will then connected to an automated ventilator (Draeger Primus®; Drägerwerk AG & Co., Lübeck, Germany).

All patients will be ventilated using a lung-protective strategy with tidal volume of 7 mL/kg, positive end-expiratory pressure of 6-8 cmH₂O, plateau pressures <30 cmH₂O, and recruitment maneuvers repeated every 30 min after tracheal intubation.⁴⁴ Maintenance of general anesthesia will include desflurane 1.0 MAC with 40% oxygen and 60% air, while intraoperative dose changes will be left to the anesthesiologist in charge of the patient. Depth of anesthesia (bispectral index-BIS, Covidien, France) will be monitored, with the target ranging between 40 and 60.^{45,46} Normocapnia will be maintained by adjusting the respiratory rate as needed, while normothermia (37°C) will be maintained throughout the intraoperative period.

All patients will be operated by at least two consultant surgeons who will be supervised by a Professor of Surgery.

Sampling and laboratory measurements

Participants will undergo sampling of peripheral venous blood, immediately after arrival to the OR, and at the Post-Anesthesia Care Unit (PACU). Blood samples drawn from all patients and EDTA plasma will be stored at -80° C until later measurement. Plasma suPAR levels will be determined using the suPARnostic® quick triage lateral flow assay (ViroGates, Denmark), according to the manufacturers instructions.

Microcirculation flow analysis

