In addition to routine hemodynamic data, sublingual microvascular flow will be measured using noninvasive technology. We will obtain measurements preoperatively (PRE), intraoperatively (INT), and postoperatively after arrival in the PACU (POST). At each time point, we will image the microcirculatory network of the sublingual mucosa with sidestream darkfield (SDF+) videomicroscopy which has an increased optical resolution resulting in one pixel recording an area of $0.56 \mu\text{m}^2$. This device uses the new SDF+ technology that allows the red blood cells to be visualised with greater accuracy and detail, which is essential for enhancing the capabilities of the analysis application.

We will use the sublingual space as the site of imaging because it shares the same embryologic origin as the splanchnic mucosa and can reflect derangements in splanchnic blood flow; impaired sublingual microcirculatory blood flow is associated with increased mortality and worsening organ failure in patients with sepsis.⁴⁷⁻⁵¹

Outcomes

The primary endpoint will be the presence of complications and/or admission to ICU and/or mortality within the first 60 postoperative days.

Secondary endpoints will be intraoperative complications (including desaturation [$\text{SpO}_2 <92\%$ for 3 minutes or more], need for unplanned recruitment maneuvers, hypotension [defined as systolic blood pressure $<90 \text{ mmHg}$ or mean arterial pressure $<65 \text{ mmHg}$ for 3 minutes or more or need of vasoactive drugs for correction], need for unplanned vasoactive drugs [need for vasoactive drugs not

planned before and/or continuous infusion], and/or acute new arrhythmia [atrial fibrillation, sustained ventricular tachycardia, supraventricular tachycardia, and/or cardiac arrest]), reintubation, hospital length of stay, and length of stay in ICU. Secondary endpoints will also include postoperative complications within 90 days after surgery defined as in the SURPAS studies,⁵²⁻⁵⁴ with the inclusion of atelectasis and ileus, resulting in 22 possible postoperative complications, as well as survival at hospital discharge, at 90 days, and at 1 year.

Data Collection and Monitoring

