Data analysis will be based on predefined data points on a prospective data collection form. The staff will be blinded to measurements until the end of the study and all data are analyzed. Clinical monitoring throughout the study will be performed to maximize protocol adherence, while an independent Data and Safety Monitoring research staff will monitor safety, ethical, and scientific aspects of the study. Data collection will include demographics, anesthesia parameters, C-reactive protein, P-POSSUM score, ACS-NSQIP score, APACHE II, SOFA, and the Charlson Age-Comorbidity Index (Charlson score).⁵⁵ We will use a SAS macro based on ICD-10 diagnoses to calculate the Charlson score.^{56,57} Two other simpler models adding predictive value to the ASA classification will be also used; the Surgical Mortality Probability Model and a similar model proposed by Glance and Donati.^{58,59}

Data management

The goal of the clinical data management plan is to provide high-quality data by adopting standardized procedures to minimize the number of errors and missing data, and consequently, to generate an accurate database for analysis. Remote monitoring is performed to signal early aberrant patterns, issues with consistency, credibility and other anomalies. Any missing and outlier data values are individually revised and completed or corrected whenever possible.

Sample size and predefined statistical analysis plan

Patients will be consecutively included during the study period, in a convenience sample and will be stratified into low-risk or high-risk groups, according to suPAR level (suPAR_{high} above and suPAR_{low} below 5.5 ng/ml), respectively.⁶⁰ An a priori power analysis was done set to detect a difference of 0.50 on the suPAR (between suPAR_{high} and suPAR_{low} group, based on the researchers' preference. The number of patients planned for recruitment was rounded up to 100 to allow for flexibility in the study. This sample size was estimated to achieve 80 percent power to detect the suggested difference. The sample size calculation was made using G*Power 3.1.⁶¹ The association between ASA classification, suPAR level, CRP and the rate of postoperative complications will be analyzed with logistic regression and Cox regression analyses, estimating odds ratios (ORs) and hazard ratios (HRs).

Ethics and dissemination

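### The aim is prediction, but the planned regression yields only ORs and HRs for ASA, suPAR and CRP: as written it measures neither discrimination nor what suPAR adds to age or the collected risk scores

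*Combined protocol and SAP*

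**What the plan says.** The Aim section asks whether suPAR, measured before and immediately after surgery, "can predict the risk of future complications and post-operative mortality in adults following major non-cardiac surgery". Under Outcomes: "The primary endpoint will be the presence of complications and/or admission to ICU and/or mortality within the first 60 postoperative days".

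The section Sample size and predefined statistical analysis plan contains three things: patients "will be stratified into low-risk or high-risk groups, according to suPAR level" at 5.5 ng/ml; a power statement for 100 patients; and the sentence "The association between ASA classification, suPAR level, CRP and the rate of postoperative complications will be analyzed with logistic regression and Cox regression analyses", with ORs and HRs as the output. It does not say whether ASA, suPAR and CRP enter one model or separate ones. It does not tie the regression to the 60-day composite, and it does not say which of the two suPAR samples is used.

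Data Collection and Monitoring lists far more than the regression uses: "Data collection will include demographics, anesthesia parameters, C-reactive protein, P-POSSUM score, ACS-NSQIP score, APACHE II, SOFA, and the Charlson Age-Comorbidity Index". It adds: "Two other simpler models adding predictive value to the ASA classification will be also used". It does not say how those models will be used, whether suPAR is added to or compared with them, or by what measure.

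**The concern.** A prediction question needs a measure of how well the marker separates patients who have the outcome from those who do not. An OR or HR does not supply one. No AUC, C-index, sensitivity, specificity or comparison of models without and with suPAR is planned anywhere.

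Age, ASA class and the clinical scores need no new blood test, so a clinician will want to know what suPAR tells them beyond these. The protocol points to that question itself:

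- The Background says the baseline suPAR level rises with age and ranks suPAR against age as a mortality marker.
- It cites age-adjusted analyses, and argues for suPAR over an existing triage system with an AUC of 0.84 against 0.62.
- The source cited for the 5.5 ng/ml cut describes suPAR in its title as an addition to existing preoperative risk assessments (reference 60).

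With age and the scores outside the named terms, the planned output cannot answer it. If a significant suPAR OR were later presented as added value, part or all of it could be age.

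**Working it through.** **The plan's own figure.** The only figure in the analysis section is 100 patients for 80% power to detect a difference of 0.50. Alpha, sidedness, SD and allocation are not given. Read as 0.50 SD with two equal groups and alpha 0.05, the total is 126 (normal approximation) or 128 (t-test) two-sided, and 100 or 102 one-sided. The figure concerns a difference between suPAR groups, not discrimination or an adjusted OR, and nothing below depends on it except N = 100.

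**1. An OR does not fix discrimination.** For a marker split at a cut, AUC = (sensitivity + specificity)/2. Assume OR 3, 20% events below the cut and 20% of patients above it.

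- Odds above the cut = 3 × 0.25 = 0.75, so the risk there is 0.75/1.75 = 0.429.
- Overall event rate = 0.2 × 0.429 + 0.8 × 0.2 = 0.246.
- Sensitivity = 0.0857/0.246 = 0.35; specificity = 1 - 0.2 × 0.571/0.754 = 0.85; AUC = 0.60.

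With 10% or 30% of patients above the cut, the same OR gives AUC 0.56 or 0.62 and sensitivity 0.19 or 0.48.

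**2. What omitting age could do.** The documents give no event rate, age-suPAR correlation or age effect, so every input is assumed: N = 100, 25% events, ASA OR 1.5 per SD, CRP correlated 0.3 with suPAR, and suPAR carrying nothing beyond age. Logistic simulation, 4000 runs per cell. Ranges are over ASA-age correlations of 0.1 to 0.5.

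| Age-suPAR correlation | Age OR per SD | suPAR significant: ASA + CRP + suPAR | With age added |
|---|---|---|---|
| 0.2 | 1.5 | 5-6% | 5% |
| 0.2 | 2.0 | 7-8% | 5-6% |
| 0.3 | 2.0 | 9-12% | 5% |
| 0.5 | 1.5 | 9-11% | 4-5% |
| 0.5 | 2.0 | 15-25% | 4-5% |

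An independent re-run with 3000 runs per cell agreed within simulation error. If suPAR is modelled alone, which the text allows, the last row becomes about 27-37% and the 0.2 rows about 6-9%. These are errors only for a claim that suPAR adds to age.

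**3. How much discrimination a real effect buys.** With age, ASA and CRP as the base and 25% events, a true adjusted suPAR OR of 1.5 per SD raises the AUC from about 0.70 to 0.72. An OR of 2.0 raises it from about 0.715 to 0.76. The OR alone shows neither gain.

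**4. Precision available.** Hanley-McNeil: SE² = [A(1-A) + (n₁-1)(Q₁-A²) + (n₀-1)(Q₂-A²)]/(n₁n₀), with Q₁ = A/(2-A) and Q₂ = 2A²/(1+A). For A = 0.70, Q₁ = 0.538 and Q₂ = 0.576. With 25 events: SE² = (0.21 + 24 × 0.0485 + 74 × 0.0865)/1875 = 0.00414, SE = 0.064, 95% half-width 0.13. With 10 and 40 events the half-widths are 0.19 and 0.11.

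Simulated power for an age-adjusted suPAR OR of 1.5 / 2.0 per SD (age-suPAR correlation 0.4, ASA-age correlation 0.3, age OR 1.5) is 16%/37% at 10% events, 29%/62% at 25% and 35%/73% at 40%.

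**5. Continuous suPAR against the 5.5 ng/ml split.** The share above the cut is unknown. Under suPAR in surgery, the protocol gives gastric cancer values of 4.8 ± 4.4 and 7.0 ± 6.1 ng/mL. Assuming lognormal values, σ² = ln(1 + (SD/mean)²) and μ = ln(mean) - σ²/2.

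- First group: σ² = 0.610, μ = 1.264, P(>5.5) = 1 - Φ((1.705 - 1.264)/0.781) = 29%.
- Second group: σ² = 0.565, μ = 1.663, P(>5.5) = 48%.

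At those shares, split power for OR 2.0 and 25% events is about 41-47%, against about 62% for continuous suPAR. If only 5-20% exceed the cut, as the 3-4 ng/mL quoted for unselected emergency patients might suggest, it is about 20-39%.

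**The case against.** The strongest reply is that the protocol never claims added value. The Aim speaks of predicting risk, not of predicting beyond age or the scores, and the analysis sentence calls its output an association. The support for an added-value question comes from background accounts of other studies and from the title of a source that cannot be consulted here. The text on the two further models and the age-comorbidity index also suggests that some use of the scores is intended but not described.

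Much of this stands. The plan's OR is not invalid, and nothing shows a deliberate choice to ignore age. The part on discrimination is better grounded than the part on age, because it follows directly from the Aim. But the section is headed as a predefined analysis plan, and the sentence on the further models sits under data collection with no comparison and no metric. Followed as written, the plan produces neither quantity.

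Two stronger readings are tempting and are not supported:

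- A reader might infer that the planned test has a false-positive rate of up to 25%. That needs a correlation of 0.5 and an age OR of 2.0 together, in a joint model, and a claim the protocol does not make. At a correlation of 0.2 the excess over 5% is 0 to 3 points.
- A reader might infer that the 5.5 ng/ml split is close to useless. The protocol's own surgical cancer values put 29-48% above the cut, where the loss of power is moderate.

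It is also fair to say that 100 patients will not measure a gain in AUC well. In simulation at 25% events, the interval for the gain excluded 0 in only about 10% of studies for a true gain of 0.02 and about 30% for 0.04.

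**Conclusion.** The point holds in this form. The plan sets out to test prediction, but its only regression analysis reports ORs and HRs for three variables. It gives no discrimination measure, and it leaves out age and the collected scores. The discrimination gap rests on the text alone. The size of any age effect rests wholly on assumed inputs, and no figure in the documents places the study at either end of the 5-25% range. This is a worthwhile, cheap improvement and does not show that the planned estimates are wrong.

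**What to change.** For the 60-day primary composite, prespecify:

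1. The AUC with 95% CI of preoperative suPAR alone, and its sensitivity and specificity at the planned 5.5 ng/ml cut.
2. One logistic model with age, ASA (one linear term), CRP if it is measured preoperatively (the plan does not give its timing, so state it), and continuous preoperative suPAR. Use a penalised method such as Firth, because events may be few.
3. The optimism-corrected AUC of that model without and with suPAR, and the difference with a bootstrap CI, presented as estimates and not as a test.

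Use the same terms in a Cox model for time to the first component of the composite, with the C-index. As secondary analyses, use the 5.5 ng/ml split in the adjusted model, the PACU suPAR value in place of the preoperative one, and suPAR added to one collected preoperative risk score named in advance, for example ACS-NSQIP.

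The cost is one more model term and analysis work on data already collected. With four terms, 10 to 40 events give 10/4 = 2.5 to 40/4 = 10 events per parameter. Given the half-widths and power shown above, the plan should state that a null age-adjusted result will not be read as evidence that suPAR adds nothing.
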